7.2 Data Clarification and Correction

Once entered, data will be evaluated to ensure that it is complete, consistent and logically sound. Data changes or query resolution within the CDMS will be addressed at the site level. All changes, reasons for changes, and persons making the changes will be captured in the system's audit trail.

7.3 CRF Completion Schedule

All CRFs should be completed within 14 working days of each visit.

8.0 Risk Assessment

Possible benefits and risks associated with the study procedures and device placement are outlined in the IRB-approved informed consent form.

Some risks are possible with transcatheter approaches, including:

- access site complications
- incomplete closure of the defect
- repeat procedure to the septal defect
- air embolism
- myocardial infarction
- pericardial tamponade
- cardiac arrest
- renal failure
- sepsis
- significant pleural or pericardial effusion requiring drainage
- significant bleeding
- endocarditis
- headache or migraine
- Transient Ischemic Attack (TIA) or stroke
- death
- cardiac arrhythmias
- thromboembolic events

Risks specific to the GORE® Septal Occluder device include, but are not limited to:

- unsuccessful device delivery

CONFIDENTIAL INFORMATION

- fracture of the wire frame resulting in device instability or other clinical sequelae
- occluder disc expansion resulting in clinical sequelae or intervention
- possible allergic reaction to nickel in wires
- perforation of cardiac tissue by the device
- enlargement of the defect during or after device deployment
- embolization of the implant
- surgical intervention to correct device failure
- insufficient closure of the defect

8.1 Minimization of Risks

Potential risks associated with the use of the GORE® Septal Occluder will be minimized by the following:

- W. L. Gore & Associates, Inc. has performed qualification testing on the device and device components and appropriate quality control measures have been implemented into production.
- Investigators will be selected who are knowledgeable and experienced in transcatheter closure of ostium secundum atrial septal defects.
- Comprehensive site Investigator and staff training will be conducted to share information regarding the design of the occluder, its application, and preliminary clinical results from any pre-clinical and clinical studies.
- The site Investigator, Co- and/or Sub-Investigators, clinical study coordinator(s) or designee at each participating site will be trained to the protocol, reminded of the importance of patient selection and specific anatomy criteria when using the occluder, and subject follow-up requirements.
- Protocol inclusion/exclusion criteria and follow-up schedule were designed to select appropriate subjects and identify potential complications early.
- Subjects will be assessed post-procedure and subsequently on a regular basis to collect information on the subject's status and any reportable adverse events.
- Data completed by the clinical sites will be monitored. An initiation site visit and interim site visit(s) will be conducted as appropriate to evaluate protocol compliance and to evaluate the data for accuracy and subject safety.
- Safety and efficacy data obtained during the clinical study will be shared with the site Investigators to aid understanding of the device and potential complications associated with its use.

CONFIDENTIAL INFORMATION

- An evaluation will be completed by the Investigator for each subject against the inclusion/exclusion criteria before study entry to ensure the subject's defect and anatomy is appropriate. Procedural echocardiographic or other appropriate imaging will be used to assess the subject defect suitability.
- Antiplatelet therapy will be prescribed for 6 months post index procedure to reduce the risk of thrombosis. Peri-procedural antibiotics prophylaxis is recommended to reduce the risk of infection.
- All protocol defined echocardiographic images will be reviewed by the Echocardiography Core Laboratory to evaluate the heart and any residual shunting across the ASD.
- Risk of device embolization has been minimized in two ways. First, the device is designed with a retrieval function. The ability to retrieve the device is maintained until the Investigator ensures proper fit into the defect. Additionally, the occluder size selected for the defect is recommended to be approximately 1.75:1 (device nominal diameter-to-defect diameter) and defects not greater than 17mm will be treated in this protocol. An occluder that pulls through the defect after left or right atrial disc conformation may be too small and should be removed and replaced with a larger size.

8.2 Summary of Expected Benefits

The expected benefit to the patient from the use of the GORE® Septal Occluder in the treatment of *ostium secundum* atrial septal defects is to reduce or arrest the shunting between the atria, to arrest or reverse the associated right heart and pulmonary pathology, and to have a short hospital stay and return to normal activity within two weeks of the procedure.

9.0 Adverse Events and Safety Monitoring

An adverse event (AE) is defined as any untoward medical occurrence in a subject whether device related or not.

9.1 Anticipated Adverse Events

A list of benefits and risks associated with the procedure- and device-related complications that may be anticipated in subjects undergoing transcatheter *ostium secundum* ASD closure are identified in Section 8.0, Risk Assessment. These pre-defined complications are considered anticipated AEs. If a complication occurs that is not on the list of known, potential complications and the Investigator believes that the complication is a potential UADE (see

CONFIDENTIAL INFORMATION

section below), the site should immediately contact the Sponsor to determine reporting requirements.

The Investigator at each investigative site is ultimately responsible for reporting AEs to the Sponsor. The Investigator or designee is required to complete the appropriate CRFs to report the occurrence of AEs.

9.2 Unanticipated Adverse Device Effects

An unanticipated adverse device effect (UADE) is defined as “any serious adverse effect on health or safety or any life-threatening problem or death caused by, or associated with, a device, if that effect, problem or death was not previously identified in nature, severity, or degree of incidence in the investigational plan or application (including a supplementary plan or application), or any other unanticipated serious problem associated with a device that relates to the rights, safety, or welfare of subjects” (21 CFR Part 812.3).

“An Investigator shall submit to the sponsor and to the reviewing IRB a report of any unanticipated adverse device effect occurring during an investigation as soon as possible, but in no event later than 10 working days after the Investigator first learns of the effect” (21 CFR Part 812.150). All UADEs must be documented by the Investigator including the date of onset, a complete description of the event, possible reason(s) for the event, severity, duration, actions taken and outcome. Copies of all supporting documents will be uploaded into the CDMS concurrently with the appropriate CRF. A report from the Sponsor will be submitted to the FDA and to all reviewing IRBs and participating Investigators within 10 working days after the sponsor first receives notice of the effect.

9.3 Adverse Event Relationship

Each reported AE will be assessed by the Investigator for its suspected relationship to the occluder device, interventional procedure, and/or study medications. Each relationship will be defined as either: definitely related, probably related, possibly related, unrelated, or unknown.

9.4 Serious Adverse Events

Each AE will be assessed by the Investigator for seriousness. Each AE is categorized as either Serious or Non-Serious. A Serious Adverse Event (SAE) is an adverse event that:

1. led to a death;
2. led to a serious deterioration in health of a subject that:
 - results in a life threatening illness or injury;
 - results in a permanent impairment of a body structure or body function;

CONFIDENTIAL INFORMATION

- requires inpatient hospitalization or prolongation of existing hospitalization;
- results in medical or surgical intervention to prevent permanent impairment to body structure or a body function; or

3. led to fetal distress, fetal death or a congenital abnormality/birth defect.

9.5 Adverse Event Severity

Each AE will be assessed by the Investigator for severity. The severity describes the maximum intensity of the adverse event; for purposes of consistency, these intensity grades are defined as follows:

Mild	Does not interfere with subject's usual function
Moderate	Interferes to some extent with subject's usual function
Severe	Interferes significantly with subject's usual function

Note the distinction between the severity and the seriousness of an adverse event. A severe event is not necessarily a serious event. For example, a headache may be severe (interferes significantly with subject's usual function) but would not be classified as serious unless it met one of the criteria for seriousness, as described in section 9.4.

9.6 Adverse Event Data Collection

All study AEs will be collected, recorded on the appropriate CRF, maintained in the CDMS, and documented in the subject's permanent medical record.

Adverse event reporting requirements are as follows:

- Adverse Event Name
- Adverse Event Onset Date
- Severity (see Section 9.5)
- Primary Relationship (see Section 9.3)
- Seriousness (see Section 9.4)
- Treatment
- Action Taken
- Outcome
- Adverse Event Resolution Date
- If applicable, was AE cause of death.

Adverse Event Submission Guidelines:

- Adverse event reporting begins once the patient is enrolled in the trial. All adverse events should be reported from enrollment through study completion/discontinuation.
- An adverse event that changes from non-serious to serious should be reported as a new adverse event.
- Adverse events with an outcome status of "Ongoing" should be assessed at each follow-up evaluation to determine if the event

CONFIDENTIAL INFORMATION

has resolved. Adverse events ongoing at study completion/discontinuation should be left as “Ongoing” on the AE case report form.

- Provide a diagnosis if possible. If unable to provide diagnosis, report the symptoms as separate events. Adverse Events should be reported without abbreviations or narratives.
- If a subject dies while on study, the cause of death will be reported as the adverse event and “death” reported as the event outcome on the AE case report form. If the subject has other ongoing adverse events at the time of death, the outcome status of those events should be reported as “death” on each AE case report form.

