4.1 Inclusion Criteria

All responses must be Yes to be eligible.

1. Patient has an *ostium secundum* ASD with evidence of right ventricular volume overload.
2. Patient has a defect size of ≤ 17 mm as measured directly by stop flow balloon sizing.
3. Patient vasculature is able to accommodate the delivery system and/or procedural accessories.
4. Patient is able to accommodate TEE or ICE probe for implant procedure.
5. Patient is judged to have adequate septal rims to retain the device.
6. Patient (or legal guardian, if subject is a minor) must voluntarily sign a Patient Informed Consent Form specific to the study. The Patient Informed Consent Form must be reviewed and approved in a manner that complies with requirements of the hospital's Institutional Review Board.
7. Patient (and legal guardian, if patient is a minor) must be physically and mentally willing to comply with all study follow-up

CONFIDENTIAL INFORMATION

requirements through 36 months, including routinely scheduled diagnostic testing and physical examinations.

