5.4.3 Enrollment

A subject is considered enrolled into the clinical study when the GORE® Septal Occluder device is introduced into the anatomy of the subject. Subjects who enroll in the trial and have a successful implant should be followed through 36 months post index procedure (see Study Schema, Section 5.1).

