5.4.4 Transcatheter Procedure

Subjects will be consented to the GORE® Septal Occluder Study prior to transcatheter procedure.

Subjects will undergo placement of the GORE® Septal Occluder via a transcatheter procedure. During the transcatheter procedure either transesophageal echocardiography (TEE) or intracardiac echocardiography (ICE) will be performed with general anesthesia or conscious sedation based on the institution or Investigator's general practice. These are acceptable testing modalities during the transcatheter procedure. Procedure time begins upon venous cannulation and procedure time ends upon removal of the final catheter.

At that time, under general anesthesia or conscious sedation and by utilizing transesophageal echocardiography (TEE) or intracardiac echocardiography (ICE), either TEE or ICE static sizing and stop flow balloon sizing of the defect takes place. Static and stop flow balloon defect sizing of 17 mm or less and cardiac anatomy will determine final patient suitability and the appropriate device size for closure of the defect.

Data will be recorded to characterize the procedure.

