10.2 Sample Size Assumptions

The safety and efficacy of the GORE® Septal Occluder will be evaluated by comparing this device to the currently marketed GORE® HELEX® Septal Occluder. To develop a control population for comparison to the GORE® Septal Occluder, an analysis of previous GORE® HELEX® Septal Occluder clinical studies was evaluated. The studies utilized included the HELEX® Device Continued Access Study (HLX 03-01) and HELEX® Device Post Approval Study (PAS HLX 06-04) as these were studies of the currently marketed implantable portion of the HELEX device (subsequent modifications to the delivery system have been made). The subject population in the HELEX device studies was limited to those subjects who would satisfy the defect size criteria for this study, specifically with defects ≤ 17 mm.

Table 10.2.1 presents the outcomes from the analysis of the HELEX device studies. Using the primary endpoint definition described in Section 3.2.3, the composite Clinical Success rate in the HELEX device studies was 86.6%.

Table 10.2.1
Composite Clinical Success with the GORE® HELEX Septal Occluder
GORE® HELEX Device Continued Access and Post-Approval Studies

	GORE® HELEX Septal Occluder
Subjects with Deployment Attempt	
Procedure Technical Success	
Implant Successful	
Implant Unsuccessful	

CONFIDENTIAL INFORMATION

Safety Outcomes at 6 Months	
Serious AE: Day 0-30	[REDACTED]
Device Embolization	[REDACTED]
Device Removal	[REDACTED]
Other ASD Reintervention	[REDACTED]
Other Serious Adverse Event	[REDACTED]
Device Embolization: Day 31-182	[REDACTED]
Device Removal: Day 31-182	[REDACTED]
Other ASD Reintervention: Day 31-182	[REDACTED]
Overall	[REDACTED]
Defect Closure Status at 6 Months (Core Lab)	
Occluded	[REDACTED]
Clinically Insignificant	[REDACTED]
Clinically Significant	[REDACTED]
Not Completed	[REDACTED]
Composite Clinical Success at 6 Months	
Success	[REDACTED]
Failure	[REDACTED]
Not Evaluated	[REDACTED]

10.3

Non-Inferiority Margin

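### Adverse event reporting starts when the occluder enters the body, after venous access and required balloon sizing; this conflicts with the schedule and the SAE endpoint and can leave procedural SAEs unreported

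*Combined protocol and SAP*

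**What the plan says.** All references are to the combined protocol and SAP.

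- **Start of reporting.** Section 9.6: "Adverse event reporting begins once the patient is enrolled in the trial", followed by "All adverse events should be reported from enrollment through study completion/discontinuation".
- **Enrolment.** Section 5.4.3: "A subject is considered enrolled into the clinical study when the GORE® Septal Occluder device is introduced into the anatomy of the subject".
- **Order of the procedure.** Section 5.4.4 places consent first ("Subjects will be consented to the GORE® Septal Occluder Study prior to transcatheter procedure") and then defines the procedure: "Procedure time begins upon venous cannulation and procedure time ends upon removal of the final catheter". It adds: "Static and stop flow balloon defect sizing of 17 mm or less and cardiac anatomy will determine final patient suitability". The same sentence makes sizing the basis for choosing the device size.
- **Sizing as eligibility.** Section 4.1 requires: "Patient has a defect size of ≤ 17 mm as measured directly by stop flow balloon sizing".
- **Schedule.** The adverse event row in section 5.2 is marked in the Procedure column and not in the Screening column.
- **Endpoints.** The primary composite (section 3.2.1) requires freedom from any SAE up to 30 days after the procedure and gives no starting point. The Safety endpoint (section 3.2.2) counts SAEs in the first 30 days.
- **No device attempt.** Under section 5.4.2, consented patients in whom no placement is attempted are screen failures without follow-up. The intent-to-treat population in section 10.6.2 consists of enrolled subjects only.
- **Historical control.** Table 10.2.1 has a row "Serious AE: Day 0-30" in a table whose first row counts subjects with an attempted deployment. The counts are redacted.

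**The concern.** Section 9.6 is the instruction that sites follow when deciding what to enter. If they follow it as written, the first part of the index procedure lies outside adverse event reporting: venous access, catheter manipulation and balloon sizing. Section 8.0 lists access site complications, air embolism and arrhythmia among the risks of transcatheter approaches, and any of these can begin before the occluder is introduced. Section 9.3 asks investigators to judge relationship to the interventional procedure, which suggests that procedural events were meant to be captured.

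Three uses of the data are affected: the 30-day SAE component of the primary composite, the Safety endpoint, and the 30-day analysis of 50 pivotal subjects that must be accepted before Continued Access enrolment starts (sections 10.5 and 10.6.1). With up to 21 sites, the conflict may also be resolved differently from site to site. The reporting fields in section 9.6 include an onset date but no onset time, so events before and after device introduction on the index day could not be separated afterwards from those fields.

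**Working it through.** **1. Order of events.** Consent, then venous cannulation (procedure time starts), then static and balloon sizing, then choice of device size, then device introduction (enrolment, and the start of reporting under 9.6). Sizing must precede introduction because it determines suitability and device size. The gap therefore runs from cannulation to device introduction, after consent and inside the procedure.

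**2. Which events fall in the gap.**

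| Event | Under 9.6 as written |
|---|---|
| Already serious before introduction; subject then enrolled | Need not be reported |
| Begins before introduction, becomes serious afterwards | Reportable: 9.6 treats a change to serious as a new event |
| Begins after introduction | Reportable |
| Serious event during sizing; no device attempted | Not collected; patient is outside every analysis population |

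**3. The plan's own figure.** Inputs from section 10.4: n_C = 253, P_C = P_T = 0.866, margin 0.10, alpha 0.05, applied one-sided through the −1.64 cut-off in section 10.6.3.

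SE = √(0.866 × 0.134/253 + 0.866 × 0.134/135) = 0.0363

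Power = Φ(0.10/0.0363 − 1.645) = 0.866, against the stated 0.86 or more. Enrolment: 135/0.9 = 150, as stated. The sample size reproduces and is not in dispute.

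**4. Value of one missed event.**

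- Clinical Success at 135 evaluable: 1/135 = 0.74 points, if the SAE is that subject's only failure. Against the 10-point margin, 0.74/10 = 7.4% of the margin.
- Pivotal safety rate at 50: 1/50 = 2 points, if the subject has no other qualifying event.

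**5. Conditional sensitivity.** The documents give no rate of serious events before device introduction. Suppose a share u of test subjects fail only through such an unrecorded event, and suppose HELEX events were fully counted. Both are assumptions. Set the true test rate at the margin, 86.6% − 10% = 76.6%, so the recorded rate is 76.6% + u. The chance of wrongly concluding non-inferiority is Φ(u/SE − 1.645), with

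SE = √(0.866 × 0.134/253 + p(1 − p)/n_T), p = 0.766 + u.

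| Assumed u | n_T = 135 | n_T = 360 (400 × 0.9) |
|---|---|---|
| 0 | 5.0% | 5.0% |
| 0.5% | 6.4% | 6.9% |
| 1% | 8.0% | 9.4% |
| 2% | 12.3% | 16.2% |
| 3% | 18.2% | 25.8% |

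At n_T = 135, u = 1% is 1.35 subjects and u = 3% is about 4. If HELEX capture began at the same point, the omission applies to both groups and this table does not describe the result.

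**The case against.** The strongest reply is that the documents do not clearly exclude these events. Section 5.2 calls for adverse event assessment at the procedure, section 5.4.4 starts procedure time at cannulation, section 9.3 provides for procedure-related events, and the composite in section 3.2.1 covers any SAE with no start point. A site reading these together could report everything from cannulation. This stands as far as it goes: the defect is a conflict between sections. It does not remove the problem, because 9.6 is the specific reporting rule and states a different start.

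The affected set is also narrow. Later complications of access or sizing are captured, and a serious event during sizing may mean that no device is introduced. Perforation should not be counted among the events at risk: section 8.0 lists it only as perforation by the device, which cannot precede introduction.

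A reader might infer that HELEX was counted from the start of day 0 and that the comparison therefore favours the new device. The documents do not support that. Day 0 is a calendar day, and section 5.4.10 also counts this study's intervals in calendar days from the index procedure. The HELEX denominator is subjects with an attempted deployment, which resembles enrolment here, so HELEX may have the same gap. Moving only the new device's clock, without knowing the HELEX start, could itself create a mismatch. Keeping the denominator unchanged does not answer this, because comparability also concerns which events enter the numerator.

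Finally, the pivotal analyses and the secondary Safety endpoint are descriptive (sections 10.6.1 and 10.6.4), so no formal test rests on them. An incomplete description is still what would be submitted for the decision to expand enrolment.

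**Conclusion.** The point holds as a conflict in the reporting rule. Section 9.6, combined with 5.4.3, starts adverse event reporting later than the schedule and the primary endpoint imply. Followed literally, it can miss events already serious before device introduction in subjects who are then enrolled, and it collects none from consented patients who had balloon sizing without a device attempt.

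The size per event is small and known, as shown in step 4 of the working. The total is unknown, because no pre-introduction event rate is given and the HELEX counts are redacted. The type I error figures show what would follow under assumed shares with complete HELEX capture; they are not estimates for this trial.

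Neither a bias in the non-inferiority comparison nor its direction is established. Nor do the documents support saying that these events cannot fail the composite; that depends on which section a site follows. What remains whatever HELEX did is that procedural safety of the new device may be under-reported in absolute terms, and that a comparison with historical data has no stated, matched start for its SAE window.

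**What to change.** 1. In section 9.6, for every subject who becomes enrolled, require adverse event reporting from venous cannulation of the index procedure, and record whether onset was before or after device introduction. State the same start in section 3.2.1 and in the note to the schedule.
2. Leave the enrolment definition and the analysis denominator as they are.
3. In section 10.2, state when SAE capture began in the HELEX studies. If it began later than cannulation, also present the primary comparison with this study's events restricted to the matching start; the onset flag makes this possible.
4. List separately, outside the endpoint, procedural SAEs in consented screen failures who underwent balloon sizing.

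The cost is protocol and CRF-guideline wording, one added field, a few more event entries and a check of the HELEX study records. No visits are added. The recorded SAE rate may be slightly less favourable.
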